fails to activate when required, as often observed in substance use disorder, target neurons in the NAcc core do not receive critical information needed to select the appropriate outcome, causing acquired maladaptive response patterns to persist (e.g. drug consumption). Higher FC between DLPFC and NAcc may be achieved by stimulating DLPFC while subjects perform tasks that require cognitive flexibility, an aspect of executive functioning.

Transcranial direct current stimulation (tDCS) has shown in both healthy subjects and in patients (e.g. Parkinson's disease, stroke, and depression) to modulate synaptic strengthening and neurotransmitter-dependent plasticity underlying changes in behavior and learning. It therefore has the potential to increase functional connectivity between NAcc and DLPFC when paired with a cognitive task engaging this pathway. As previously described, strengthening this pathway should facilitate proper selection of goal-directed behavior and decrease craving in those with substance use disorder.

There is currently limited data regarding the efficacy of tDCS on smoking cessation and no data regarding the efficacy of combining tDCS with a concurrent task requiring cognitive flexibility. Although studies have assessed the effect of tDCS on smoking behavior, these have not combined stimulation with a task requiring cognitive flexibility nor have these studies assessed cessation outcomes. Instead, smoking cues were presented either immediately prior to, during or immediately after neurostimulation with the outcomes assessed being either cue induced craving severity, number of cigarettes smoked during the days of stimulation or using laboratory based smoking choice paradigms. These studies have generally found small but positive effects in these measures. However by not combining tDCS with the cognitive flexibility task, these studies may not have been able to maximize the effects of this intervention.

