## 3.0 Study Endpoints/Events/Outcomes

- **3.1** Primary Endpoint/Event/Outcome: As a pilot study, the main objective of this investigation is to determine the feasibility of using the proposed approach as a method by which to increase smoking cessation rates. The primary endpoint is therefore to determine if recruiting smokers into a study evaluating tDCS will be feasible and if the intervention is well tolerated by smokers.
- 3.2 Secondary Endpoint(s)/Event(s)/Outcome(s): Secondary endpoints include measures associated with smoking cessation outcomes including time to smoking lapse, time to smoking relapse, number of cigarette smoked, severity of craving and severity of withdrawal symptom score. We will also assess impulsivity as tDCS may impact this measure. fMRI measures will be assessed in the subpopulation of subjects enrolled after protocol revision # 3 is approved and after all preparations to enroll subjects into this portion of the study are complete.

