#### 5.0 Procedures Involved

- **5.1** Study Design: This study is a randomized double-blind pilot study in which subjects will receive either active or sham tDCS
- **5.2** Study Procedures: The following procedures will occur during the study
- 5.2.1 Screening visit: Initial eligibility will be assessed via a phone interview. Those likely to qualify will be scheduled for a screening visit at which written informed consent will be obtained and eligibility confirmed. Medical, psychiatric and smoking history will be obtained via subject report with smoking status biochemically confirmed (via an exhaled carbon monoxide (CO) concentration of > 8 ppm or a urinary nicotine test strip = 6). Baseline levels of a variety of measures such as severity of smoking urges, severity of withdrawal symptoms, extent of nicotine dependence and how subjects evaluate their current cigarettes will be assessed via questionnaires. Height and weight will be measured. Those who qualify will be scheduled for a week during which they will come in daily for 5 consecutive days to receive tDCS treatments (active or sham) and will be asked to maintain a daily tobacco use diary in order to assess baseline levels of smoking. Subjects enrolled after revision # 3 has been approved and all preparations to enroll subjects into the scanning portion of the study are complete will be asked to come in for two additional visits to collect fMRI data: one visit before tDCS treatments begin, and a second visit after all tDCS treatments are completed.
- 5.2.2 MRI scanning visits (2 visits, 1 visit occurring during the week prior to and the other visit occurring during the week following the tDCS visits): Participants will undergo an MRI scan (3T), which takes about 75 to 80 minutes. MRI involves taking pictures of the participant's brain, from which the properties of certain brain tissues can be measured. These scans are strictly for research

purposes and therefore will not receive a clinical or medical interpretation. For the scan, the participant will be asked to lie down quietly on a bed, and the bed will slide into the scanner. Once the participant is inside the scanner, the imaging will begin. During the scan, the participant will be asked to lie quietly in the scanner with their eyes closed and may also be asked to perform a cognitive task (e.g., reversal learning task). The MRI scan will be performed at the University of Minnesota's Center for Magnet Resonance Research.

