At the beginning of each tDCS visit, participants will be assessed for number of cigarettes smoked 24 hours prior to the session, the time since last cigarette and exhaled CO levels. A cigarette evaluation scale will be completed at each visit. Additionally, adverse events, smoking urges and nicotine withdrawal symptom severity will be assessed before and after each session using several questionnaires. At the first tDCS session, urine will be collected to be analyzed at a later time for markers of cigarette smoking (e.g., cotinine concentrations). Prior to the first and after the last tDCS session, participants will also complete an impulsiveness questionnaire as this parameter is thought to be affected by tDCS, a

questionnaire assessing nicotine dependence as well as a questionnaire assessing motivation and self-efficacy to quit smoking.  Total participation time at each visit is not expected to exceed 2 hours per day.

At these visits, participants will be provided a smoking cessation treatment manual (Clearing the Air) and begin preparation for the quit date, which will be at the end of the 5th visit. The standardized content of the brief (10 min) behavioral treatment session provided to participants will include discussing benefits of quitting, ways to prepare the environment to minimize smoking cues (e.g., removing ashtrays), and methods to reduce craving and withdrawal symptoms (e.g., deep breathing). Participants will also keep track of situations associated with smoking and begin to develop a plan to deal with these situations.

This tDCS device to be used in this study is located in the MnDRIVE Non-invasive Neuromodulation Laboratory. There is currently no evidence of serious side-effects.  Mild side-effects that typically resolve upon discontinuing tDC include light itching under the electrode at the beginning of administration, headache, fatigue, and nausea. The subject may choose to discontinue stimulation at any time during the session if experiencing excessive discomfort or side effects. Although seizures are not a known risk of tDCS intervention,  anyone with a history or a risk for seizures will be excluded from the study. No other risks related to tDCS are anticipated.

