## 16.0 Data Management

Data Analysis Plan: Data collected in this pilot study will be used as preliminary data and proof of concept to facilitate the design of and estimate power for subsequent larger grants. Descriptive statistics will conducted and effect sizes will be estimated. Linear mixed models will be used to examine time, group (sham vs. active) and group by time effects for various continuous outcome measures (e.g. craving). Survival analyses will be used to examine group differences on time to relapse to smoking.

- **16.1** Power Analysis: As this is a pilot study, no power analysis was done.
- **16.2** Data Integrity: In order to ensure that data entry is correct, data collected on paper questionnaires will be entered twice with the two entries compared and any discrepancies resolved.

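### Section 16.0 states no baseline adjustment, though craving, withdrawal and impulsivity are all scored before stimulation: an avoidable but modest loss of precision in secondary contrasts

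*Combined protocol and SAP*

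**What the plan says.** Section 16.0 of the combined protocol and SAP is the whole analysis plan. For continuous outcomes it reads: "Linear mixed models will be used to examine time, group (sham vs. active) and group by time effects for various continuous outcome measures". It adds that "effect sizes will be estimated" and that the data "will be used as preliminary data and proof of concept to facilitate the design of and estimate power for subsequent larger grants". It does not say whether a pre-stimulation score is a covariate, a level of the time factor, or left out. It also does not say which comparison, or which SD, defines an effect size.

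Section 3.2 lists "severity of craving and severity of withdrawal symptom score" among the secondary endpoints and adds: "We will also assess impulsivity as tDCS may impact this measure".

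All three outcomes have a pre-stimulation value:
- **Craving and withdrawal, at screening** (5.2.1): "Baseline levels of a variety of measures such as severity of smoking urges, severity of withdrawal symptoms".
- **Craving and withdrawal, at each tDCS visit** (5.2.3): "smoking urges and nicotine withdrawal symptom severity will be assessed before and after each session". The first before-session score is therefore a second pre-stimulation value. Four weekly post-quit scores follow (5.2.4).
- **Impulsivity** (5.2.3): one score before the first session and one after the last.

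**The concern.** Taken at face value, the planned terms lead to one of two active-versus-sham comparisons. If the pre-stimulation score is a level of time, the group-by-time contrast against it compares changes. For impulsivity, with two scores, that is exactly what it is. If the pre-stimulation score is left out, the contrast is unadjusted. Both estimate the same difference without bias under randomisation, but neither is usually the most precise use of a score already collected.

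Two further ambiguities follow from the same sentence. Craving and withdrawal can have up to 1 + 10 + 4 = 15 time levels (screening, ten session scores, four weekly visits). With categorical time the interaction is then a 14-df test and not an effect size. And if baseline is a time level, the group main effect averages in a pre-treatment score; with two levels, this halves a post-treatment effect.

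What is at stake is the precision and definition of effect sizes meant to inform the power of later studies.

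**Working it through.** **Inputs.** Section 11.1 aims for about 20 completers. The allocation ratio is not stated, so 1:1 (10 per arm) is assumed. The documents give no SD or correlation; SD is set to 1 and correlations are varied. Section 16.1 says no power analysis was done, so the plan has no figure to reproduce.

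**Formulas.** The outcome is the mean of k follow-ups, which correlate rf with each other and rb with each pre-score. The baseline is one score, or the mean of two that correlate rp.
- Unadjusted: V = (1 + (k − 1)rf)/k
- Baseline variance: B = 1 (one score) or (1 + rp)/2 (mean of two)
- Change score: V + B − 2rb
- Adjusted: (V − rb²/B) × 17/16, where 17/16 = 1 + 1/(20 − 4) is the cost of estimating the slope
- 95% half-width: t × √(0.2 × variance), with t = 2.101 (18 df) for unadjusted or change score and 2.110 (17 df) for adjusted

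**(a) Four post-quit visits, all correlations equal to r.**

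| r | Unadjusted V | Change, one pre-score | Adjusted, one | Ratio to change | Ratio to unadjusted | Change, mean of two | Adjusted, mean of two | Ratio to change |
|---|---|---|---|---|---|---|---|---|
| 0.3 | 0.475 | 0.875 | 0.409 | 0.47 | 0.86 | 0.525 | 0.358 | 0.68 |
| 0.5 | 0.625 | 0.625 | 0.398 | 0.64 | 0.64 | 0.375 | 0.310 | 0.83 |
| 0.7 | 0.775 | 0.375 | 0.303 | 0.81 | 0.39 | 0.225 | 0.211 | 0.94 |

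Example for r = 0.3 with two pre-scores: B = 0.65; change = 0.475 + 0.65 − 0.6 = 0.525; adjusted = (0.475 − 0.09/0.65) × 17/16 = 0.358.

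Half-widths in SD units at r = 0.3, 0.5 and 0.7:
- Unadjusted: 0.65, 0.74, 0.83
- One pre-score: 0.88, 0.74, 0.58 by change score; 0.60, 0.60, 0.52 adjusted
- Mean of two: 0.68, 0.58, 0.45 by change score; 0.56, 0.53, 0.43 adjusted

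**(b) Weak baseline correlation.** This is plausible because quitting falls between baseline and follow-up. Take rf = 0.7, so V = 0.775, and one pre-score.

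| rb | Change | Adjusted | Ratio to change | Ratio to unadjusted |
|---|---|---|---|---|
| 0 | 1.775 | 0.823 | 0.46 | 1.06 |
| 0.2 | 1.375 | 0.781 | 0.57 | 1.01 |
| 0.3 | 1.175 | 0.728 | 0.62 | 0.94 |

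Break-even with unadjusted is at rb = √(V/17) = √(0.775/17) = 0.21. With the mean of two pre-scores (rp = 0.7, B = 0.85), the ratios to change score at rb = 0.2 and 0.3 are 0.773/1.225 = 0.63 and 0.711/1.025 = 0.69.

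**(c) Impulsivity, one follow-up, one pre-score.** Change = 2(1 − r); adjusted = (1 − r²) × 17/16. At r = 0.3, 0.5 and 0.7:
- Change: 1.4, 1.0, 0.6
- Adjusted: 0.967, 0.797, 0.542
- Ratio to change score: 0.69, 0.80, 0.90
- Ratio to unadjusted: 0.97, 0.80, 0.54

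At r = 0.9 the ratio to change score is (0.19 × 17/16)/0.2 = 1.01, so the gain over a change score has gone.

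**(d) Choice of SD.** Take one follow-up, a raw effect of 0.5 outcome SD and r = 0.7. Dividing by the raw, change or residual SD gives d = 0.5/1 = 0.50, 0.5/√0.6 = 0.65 or 0.5/√0.51 = 0.70. At two-sided 5% and 80% power, these imply 63, 38 or 33 per arm in a later trial.

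A simulation of 40,000 replicates agreed with the one-pre-score formulas. For example, at equal correlations the ratios to change score were 0.463, 0.635 and 0.801.

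**The case against.** The strongest reply is that the plan is brief, not wrong. Section 16.0 does not exclude a model with baseline as a response and a common mean in both arms, which makes similar use of the baseline. With categorical visits, its group-by-time term already contains the post-quit contrasts. The outcomes are secondary, the endpoint in 3.1 is feasibility and tolerability, and no power is claimed. Even adjusted, the half-widths for the four-visit mean run from 0.43 to 0.83 SD in the cases above, so the pilot pins down no effect size under any reading. All of this stands, and it sets the priority.

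It also stands that the gain over a change score is much smaller if both pre-scores are averaged, and that the gain over an unadjusted contrast can be nil. The choice of SD may matter more to later planning than the choice of model, so the fix must name it.

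A reader might infer that the post-quit craving contrast is the one of new interest, because section 2.2 says of earlier tDCS smoking studies: "nor have these studies assessed cessation outcomes". In context that remark most directly supports novelty for lapse and relapse. Section 16.0 assigns time to relapse to survival analysis, and nothing in the documents ranks the week 1 to 4 average of craving first. Naming one contrast is good practice; which one is for the investigators to choose.

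The reply does not remove the central point. A pre-stimulation score is collected for each of the three outcomes, and the plan does not commit to using it in the way that is usually most precise.

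**Conclusion.** The point holds as a low-priority improvement to the analysis of craving, withdrawal and impulsivity. Under the assumptions of 10 per arm and equal correlations of 0.3 to 0.7, baseline adjustment cuts the variance of the four-visit mean by 19% to 53% against a change from one pre-score, and by 6% to 32% against a change from the mean of two. Against an unadjusted contrast, with one pre-score, the cut is 14% to 61%. With a baseline correlation of 0.2 to 0.3 and follow-ups correlated 0.7, that last gain is nil to 6%, and at zero correlation there is a 6% loss. The correlations and the 1:1 split are assumptions throughout.

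A reader might go further and infer that the planned contrasts are biased, that the plan rules out baseline adjustment, or that the trial's main conclusion is at risk. The documents support none of these. The arms are randomised, 16.0 is silent and not prohibitive, and the primary feasibility endpoint does not depend on these models.

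**What to change.** Add to section 16.0:

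> Craving and withdrawal models will include group, visit (categorical), group-by-visit, the pre-stimulation score (mean of the screening score and the before-session score at tDCS visit 1) and pre-stimulation score by visit. Impulsivity will be analysed by ANCOVA of the after-last-session score on the before-first-session score. For each outcome, one active-minus-sham contrast (for craving and withdrawal, for example, the average over post-quit weeks 1 to 4) will be reported in raw units with a 95% CI. Any standardised value will be divided by the baseline SD.

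The two pre-stimulation scores then no longer serve as levels of time. Averaging them assumes that the same instrument is used at both visits, which should be confirmed. State also which baseline SD is meant, because the SD of a two-score mean is smaller than that of a single score.

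Do not describe the covariate model and the common-baseline-mean model as equivalent when data are missing. Agreement was checked only for complete data with one follow-up, and section 13.2 foresees withdrawals and missed visits.

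The cost is wording only: no new visit, form or participant. The statistical price is one or a few degrees of freedom, and up to about 6% more variance than an unadjusted contrast if baseline turns out to be uncorrelated with the outcome.

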- 5.2.4 Post Cessation Visits (4 visits): Follow-up visits will occur at each of 4 weekly visits. At each visit, smoking diaries will be collected and exhaled CO will be measured. Urine will be collected at the week 1, 2 and 4 visits. Weight will be measured at week 1, 2, 3 and 4 visits. Questionnaire assessing craving and withdrawal symptoms severity will be assessed as will the effects that participants report from smoking (via the cigarette evaluation scale).
- **5.3** Individually Identifiable Health Information: All information is collected directly from subjects (i.e., medical records will not be requested) and this is not a treatment study. The data being collected therefore does not meet the definition of PHI.
- **5.4** Use of radiation: N/A
- **5.5** Use of Center for Magnetic Resonance Research: This study has been reviewed by the CMRR (Project Application Review System application # 5101)

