## 9.0 Study Population

- **9.1** Inclusion Criteria: To be eligible subjects must:
  - a) Be between the ages of 18 and 64
  - b) Smoke (on average) at least 5 cigarette per day
  - c) Be motivated to quit smoking
- **9.2** Exclusion Criteria: Subjects will be excluded if they:
  - a) Regularly use tobacco products other than cigarettes (> 9 times per month)
  - b) Have any major medical or psychiatric condition that is unstable and renders them unable to participate in the study.
  - c) Have any medical condition with neurological sequelae (e.g., stroke, seizures).
  - d) History of loss of consciousness of greater than 30 minutes duration or loss of consciousness with neurological sequelae
  - e) Have any medical condition or use any medication that would either increase risk of subjects participating in this study (e.g., medications that lower the seizure threshold) or that would impact measures of interest (e.g. smoking cessation medications).
  - f) Have any contraindications for MRI scanning (e.g., metal implants, pacemakers or any other implanted electrical device, injury with metal, braces, non-removable body piercings, pregnancy)
  - g) Are pregnant or planning to become pregnant during the study
  - h) Have any contraindications to tDCS (e.g., current use of pacemaker, intracranial electrodes or implanted defibrillator).
- 9.3 Screening: At the screening visit, subjects will complete a serious of questionnaires including those that ask about medical history, smoking history and motivation to quit smoking. All inclusion / exclusion will be based on self-report except for smoking status which will be confirmed via an exhaled carbon monoxide (CO) concentration of ≥ 8 ppm or a urinary nicotine test strip reading of 6. Non-pregnant status will be confirmed via a urine pregnancy test.

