#### 13.0 Withdrawal of Participants

- 13.1 Withdrawal Circumstances: Participants will be withdrawn from the study if they report any side effects of greater than moderate severity or that raise any safety concerns. Subjects may also be withdrawn from the study if they fail to follow study procedures (e.g., show up to scheduled study visits). Additionally, subjects will be told that participation is voluntary and that they may discontinue participation at any time for any reasons.
- 13.2 Withdrawal Procedures: Subjects who withdraw from the study after having received tDCS will be asked if they can be contacted by telephone to ascertain smoking status. We will attempt to contact subjects by telephone who do not show up to scheduled visit to ascertain if they wish to continue to participate in the study (and if not, why not) and to determine smoking status.

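### Do undefined lapse and relapse events, and the lack of a rule for unreached participants, undermine the planned survival analysis?

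*Combined protocol and SAP*

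**What the plan says.** Section 3.2 lists the secondary cessation outcomes, beginning "time to smoking lapse, time to smoking relapse, number of cigarette smoked". It defines neither event. The analysis plan in section 16.0 gives them one sentence: "Survival analyses will be used to examine group differences on time to relapse to smoking". That sentence covers relapse only. It gives no event definition, time origin, censoring rule or analysis set.

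The data that could determine the events are described elsewhere:

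- Section 5.2.4 has smoking diaries collected at each of four weekly visits. At the same visits, "exhaled CO will be measured. Urine will be collected at the week 1, 2 and 4 visits".
- Section 5.2.3 gives the purpose of the urine when it is first taken: "urine will be collected to be analyzed at a later time for markers of cigarette smoking (e.g., cotinine concentrations"). It also places the quit date at the end of the fifth stimulation visit.
- Section 13.2 covers people who leave or miss visits. Those who withdraw after receiving tDCS "will be asked if they can be contacted by telephone to ascertain smoking status". For the others, "We will attempt to contact subjects by telephone who do not show up to scheduled visit", partly to determine smoking status.

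The only biochemical cut-offs are for confirming smoking at screening. They read "exhaled carbon monoxide (CO) concentration of > 8 ppm" in section 5.2.1 and "exhaled carbon monoxide (CO) concentration of ≥ 8 ppm" in section 9.3.

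Section 11.1 recruits until about 20 people have completed. Section 16.1 says no power analysis was done.

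**The concern.** A time-to-event analysis needs an event, a time zero and a rule for people whose status is unknown. The plan writes down none of these. Two analysts could follow it faithfully and report different abstinence figures from the same data. One might take the first cigarette in the diary as the event; another might let a raised CO reading override the diary.

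The handling of unreached participants looks most serious. Survival software censors them at last contact by default. If people go silent because they have relapsed, censoring overstates abstinence, and by more in the arm that loses more of them. Counting them as relapsed avoids that, but it creates a difference of its own when drop-out is unequal and unrelated to smoking.

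This would matter even in a pilot, because section 16.0 intends the effect sizes to inform the power of later studies. Sampling noise shows in a confidence interval; an unstated missing-data rule does not.

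**Working it through.** The plan gives no drop-out rate, relapse rate, effect size or event count, so there is no figure of its own to reproduce. Every input below except the completer count and the follow-up length is an assumption.

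**1. One small arm under three rules.** Assume 10 people, 5 observed relapses at weeks 1, 1, 2, 3 and 4, *k* people lost at week 1, and the rest abstinent to week 4. For *k* = 2:

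- Censored (Kaplan-Meier): (8/10) × (5/6) × (4/5) × (3/4) = 40%.
- Counted as relapsed: 3/10 = 30%.
- Completers only: 3/8 = 37.5%.

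| Lost | Censored | Counted as relapsed | Completers only |
|---|---|---|---|
| 0 | 50% | 50% | 50% |
| 1 | 45.7% | 40.0% | 44.4% |
| 2 | 40.0% | 30.0% | 37.5% |
| 3 | 32.0% | 20.0% | 28.6% |

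The rule moves one arm by about 6 to 12 points. With nobody lost, a single diary abstainer contradicted by CO moves it by 1/10, or 10 points.

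**2. False difference between arms.** Assume no true effect and a constant relapse rate of -ln(0.30)/28 per day, so that 30% are abstinent at day 28 in both arms. Assume drop-out of 30% on active and 10% on sham, with nobody recovered by telephone. Where drop-out is relapse-driven, a share *d*/0.70 of relapsers goes silent and is censored at the last weekly visit. Abstinence at day 28, from a simulation of 400,000 per arm, is:

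| Cause of drop-out | Rule | Active | Sham |
|---|---|---|---|
| Relapse-driven | Censored | 48.0% | 34.9% |
| Relapse-driven | Counted as relapsed | 30% | 30% |
| Unrelated | Censored | 30% | 30% |
| Unrelated | Counted as relapsed | 0.30 × 0.70 = 21% | 0.30 × 0.90 = 27% |

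With the same cause in both arms, the difference runs from 21 - 27 = -6 to 48.0 - 34.9 = +13 points. The cause need not be the same, however. Combining the rows gives:

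- Active relapse-driven, sham unrelated: 48 - 30 = +18 (censored); 30 - 27 = +3 (counted as relapsed).
- Active unrelated, sham relapse-driven: 30 - 35 = -5 (censored); 21 - 30 = -9 (counted as relapsed).

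The range is therefore about -9 to +18. In each mixed case both rules miss the true value of 0 on the same side, so running both is a sensitivity check and does not bound the group difference.

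Telephone recovery shrinks the problem. With relapse-driven drop-out in both arms and half of the silent relapsers recovered, the censored analysis gives 37.8% against 32.4%, about 5 points. With all recovered it gives no difference.

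**3. Against the noise.** With about 20 completers, taken as 10 per arm, the standard error of a difference in proportions near 30% is √(2 × 0.3 × 0.7 / 10) = 0.205, or about 20 points. On the survival scale, with 1:1 allocation and a two-sided 5% test, 10 to 20 events give 19% to 34% power for a hazard ratio of 0.5. Reaching 80% power needs about 66 events by Schoenfeld's formula.

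**The case for a change.** The strongest case for a change is that the estimate is what this pilot delivers, and that its definition should be fixed before anyone sees unblinded data. The remedy would be cheap: a few sentences, with no new visit or sample. Unequal drop-out is also plausible, since section 13.1 withdraws people with side effects above moderate severity and stimulation has known side effects.

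Much of this stands. The events, time zero and analysis set are unwritten, time to lapse has no named analysis, and good practice would record these choices. Four things weaken the case for a required change:

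- The plan does not call for self-report only. It leaves the source of the event open while collecting CO and diaries at every follow-up visit and urine at three of the four.
- The drop-out figures say nothing about what biochemical verification would change, so they cannot support that part of the concern.
- Section 13.2 seeks smoking status from treated people who withdraw and from those who miss visits. That suggests their data are meant to be used, although the withdrawal call covers only people who have received tDCS.
- The two CO cut-offs concern eligibility at screening, not abstinence. The difference is a single symbol, is probably clerical or an effect of text extraction, and does not touch these outcomes.

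Verification has limits too. Section 9.2 allows other tobacco up to 9 times a month, which could affect urine markers and, if smoked, CO as well.

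**Conclusion.** No change to the plan follows. This is missing detail, not a rule that gives a wrong answer. The raw material for a sensible analysis is there: a fixed quit date to serve as time zero, diaries and CO at each weekly visit, urine at weeks 1, 2 and 4, and telephone follow-up. A competent analyst would state the definitions used, report how many people in each arm could not be reached, and show the result with them censored and with them counted as relapsed.

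Under the assumed 30% relapse-free and 30% against 10% drop-out, the false difference is between about -9 and +18 points. The extremes need a threefold imbalance in drop-out, a different cause in each arm and no telephone recovery, and they still fall below one standard error of about 20 points. The actual drop-out and relapse rates are unknown, so the size could be smaller or larger.

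The outcomes are secondary, no power is claimed, and the primary endpoint of recruitment feasibility and tolerability is unaffected. Anyone using the relapse estimate to plan a later trial should allow for both its imprecision and its dependence on missing status.
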